Evaluation of Triathlon
- a new total knee prosthesis system

[name], ass Prof

Department of Orthopaedics

Lund University Hospital

Dept Orthopaedics Hässleholm Hospital

29 August 2007, Region Skåne, Sweden

NCT02522728

EVALUATION OF THE TRIATHLON KNEE SYSTEM

STUDY DESIGN SUMMARY PAGE

- Prospective, comparative, **randomised**, RSA series with 2-years follow-up.
- Primary total knee replacement surgery utilising the Triathlon Knee System
- A total of 300 patients will be included in the study, with 25 patients in each group of the sub studies.
- Clinical evaluations will be required pre-operatively, per-operatively, prior to discharge and at 3 months +/-2 weeks, 1 year +/- 2 months and 2 years +/- 2 months.
- RSA (Roentgen Stereophotogrammetric Analysis) evaluation will be required prior to discharge and at 3 months +/-2weeks, 1 year +/- 2 months and 2 years +/- 2months.
- Radiographic evaluation will be required to be completed pre-operatively, prior to discharge and at 1 year +/- 2 months and 2 years +/- 2months.
- Patient outcomes assessments (KOOS and KSS) will be required to be completed pre-operatively and at 3 months +/-2 weeks, 1 year +/- 2 months and 2 years +/- 2 months

Evaluation	Pre-op	Per-op	Prior to Discharge	3 Months	1 Year	2 Years
Medical History	✓					
Operative Details		✓				
RSA			✓	✓	✓	✓
Radiographs	✓		✓		✓	✓
Clinical	✓	✓	✓	✓	✓	✓
Outcomes	✓			✓	✓	✓

1. Introduction

Total Knee Arthroplasty (TKA) is the surgical reconstruction of the knee joint in order to relieve pain, restore function and correct deformity. It is a very common surgical procedure with figures showing more than 500.000 arthroplasties performed annually world wide. Total knee arthroplasty is considered one of the most successful types of joint reconstruction in that surgical results usually meet and even exceed expectations.

Efforts to improve the outcome of total knee replacement continue today, with issues such as implant design, material biocompatibility, wear resistance and instrument design being actively researched and refined. The role of implant design is particularly well documented in the literature. The patient's demands and the refinement of surgery have increased the demands, both on the implants and development of the surgical technique.

This clinical study proposes to evaluate a new knee prosthesis system, Triathlon.

The design for Triathlon prosthesis theoretically addresses the higher expectations and higher demands the patients of today have for their implants, especially with respect to the need for deeper knee flexion and greater ease of moving into deep flexion. This knee prosthesis is designed to allow for normal knee motion and stability through 150 degree or more of knee flexion. The design allows for correct balancing with stability and deep flexion, avoiding the gap and instability the prosthesis designs of today create during deep knee flexion. This instability is due to lack of contact between the femoral and tibia component. The Triathlon design also takes the Freeman/Pinskerova findings for the epicondylar axis during flexion in consideration. The tibia design of Triathlon is addressing this with the rotary arc for the tibial insert. The rotary arc provides the design with a possibility for smooth and consistent articulation with rotation throughout the range of motion during knee flexion, even deep.

The key features for the Triathlon design are a further improvement of the Duracon design with improved femoral posterior condyle flare and the rotary arc in insert. These features work together to provide possibility for, and help, rotation during deep knee

flexion. The Triathlon femur component has been designed for an improved anatomical fit. The anterior flange has been slightly steeper (7 degrees) which minimise the risk for anterior notching. The sizing and the femoral A/P and M/L dimensions minimize the risk for prosthetic overhang as the aspect ratio (M/L & A/P) both for the femur and the tibial component have been declined.

The Triathlon design is also focused on implant longevity by a precision locking mechanism. The aim with this is to reduce the micromotion of the poly insert related to the tibial tray even further. By reducing the micromotions, problems related to back-side wear could be reduced.

Cementless prosthetic fixations have enjoyed widespread use. It is generally agreed that careful site preparation ([name], 1994) and a precise fit between the implant and bone are required. The potential advantages of hydroxyapatite (HA) (Søballe 1993) are the shortening of the time needed to achieve adequate fixation strength and stability, and increasing the strength of the bone-Implant interface (Geesink, 1995, Søballe, 1993). Up to date the most used application is a plasma-sprayed coating technique using high temperatures (ceramics), but the technique is only feasible for rough or textured surfaces. This coating has been further developed to the Peri-Apatite coating technique which has the ability to coat all exposed surfaces of a three-dimensional porous in-growth structure. In the peri-apatite process the hydroxyapatite is formed at low temperature as a product of solution precipitation.

During the last decade, roentgen stereophotogrammetric analysis (RSA) has emerged as a way to assess prosthetic fixation (Selvik 1974). The method has been used extensively both in hip and knee arthroplasty (Kärrholm, 1989, Mjöberg, 1990, Nilsson, 1992, Ryd 1992, Nilsson, 1996, Ewald 2002). It has been shown that RSA can serve as a predictor of late mechanical loosening both for knee and hip prostheses (Ryd 1995, Kärrholm 1994).

2. Objective

The objective is to investigate the clinical, Radiographic, Roentgen Stereophotogrammetric behaviour and patient outcome when using the Triathlon total knee prosthesis in a prospective randomized clinical trial.

3. Number of Subjects

300 patients in six individually randomized sub-studies (25 patients in each randomized group) will be enrolled into the study over a 12 months recruitment period per sub-study.

Each investigator will perform at least 5-10 knee arthroplasties with the Triathlon CR (learning curve) before enrolling patients in the clinical study.

Patients will be randomly allocated to one of two equally sized groups in each sub-study. Please see section 5 of this protocol for study design and section 8.3 for randomisation.

4. Length of Study

A 2-year post-operative follow-up period for each patient is required.

5. Study Design

This is a prospective, comparative, randomised single centre clinical study. The Triathlon and the Duracon Knee Systems have to be implanted for evaluation in this study. Patients will be randomised to one of two equally sized groups within each sub study. Both knee systems are commercially available. Patellae will be resurfaced if needed. All patients included in the study will meet all inclusion criterias and none of the exclusion criterias.

Ethic Committee approval for the study will be obtained by the investigator prior to starting the inclusion of patients in the study.

Patients will be considered for enrolment according to the clinical findings and subject to gaining their suitable written informed consent (see Appendix II).

The principal evaluation parameter will be the RSA. Patient outcome will be assessed by the KOOS questionnaire and the KSS. Clinical evaluation will include the chair raise test, measurement of the extension strength, and a patella evaluation. The evaluation of the Triathlon system will be carried out in several steps, described as sub-studies all including RSA-technique.

Sub-studies:

a) Triathlon versus Duracon: The Triathlon system has a heritage in the well documented Duracon system, which has shown very good results in the Swedish Knee Register. The goal with this study is to get an indication of the long-term results of Triathlon. The evaluation is carried out by a prospective randomised RSA-study with Triathlon cemented knee prosthesis versus Duracon cemented knee prosthesis

b) Triathlon Cruciate Retaining (CR) versus Triathlon Posterior Stabilized (PS): During knee prosthesis surgery the surgeon many times need to make a judgement on if to keep a defect anatomical structure or if to replace it with knee prosthesis with a design that allows for adjustment of this defect. This sub study is aimed to evaluate which prosthetic choice to be made in respect of stability, long-term results and patient outcome.

c) Triathlon PA (HA-surface) versus Triathlon Pressfit design: The goal with the uncemented technique is to reach a full integration between the bone and the prosthesis. During the last years the usage of prosthesis with hydroxyapatite surface within tooth-, mandibular-surgery, hips- and knee-joints, have increased significantly. It has been shown that a thin layer of hydroxyapatite stimulates the anchorage of the implant. The

goal with this sub study is to compare the stability of the fixation when using two different types of Triathlon un-cemented prosthesis designs. PA (HA-surface) versus Pressfit.

d) Triathlon implanted through computer assisted surgery versus conventional technique: Today's surgical technique within knee-arthroplasty has improved greatly with better instruments and more sophisticated equipment e.g. computer assisted surgery. The goal with this sub study is to evaluate if there are any advantages with computer assisted surgery together with Triathlon. The Triathlon knee system has been developed with instrumentation specifically prepared for computer assisted surgery.

e) Triathlon knee prosthesis implanted with MIS technique versus conventional technique: Today's surgical technique within knee arthroplasty is evolving towards smaller incisions and less traumatising techniques, so called Minimal Invasive Surgery (MIS). The goal with this sub study is to evaluate the advantages for the patient when using Triathlon-MIS-technique versus conventional surgical technique.

f) Triathlon Fixed versus Triathlon Mobile Bearing: This sub study is aimed to evaluate if Triathlon mobile bearing will give the patient any advantages over the Triathlon fixed bearing.

g) Triathlon Cruciate Retaining knee (CR) with a tibial keel of standard length randomised against Triathlon Cruciate Retaining knee (CR) with a tibial part with a short keel, both system will be used with cemented fixation. The short tibial keel is thought to facilitate the surgery due to easier access and better positioning possibilities. This sub-study is aimed at evaluating if the short tibial keel will have equal fixation and migration properties as the standard keel.

h) Triathlon Cruciate Retaining knee with cemented fixation randomised versus Triathlon Cruciated Retaining knee with uncemented fixation (Peri-Apatite). The aim with this sub study is to evaluate the uncemented PA knee fixation and migration properties versus the cemented version.

6. Inclusion and Exclusion criteria

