11.1 Power - statistical considerations

From previous studies the migration during the first two years for cemented prostheses has been about 1.0 ± 0.5 mm (MTPM). Suppose this migration will decrease by 50% to 0.5 ± 0.5 mm. Considering an alpha level of 0.05 and a beta level of 0,20 (power \approx 80%) this will require 17 cases in each group. With a β of 0,75, 15 patients in each group will be needed. Continuous migration between the 1st and 2nd year follow-up has been found in up to 50% of the cases. Suppose that an improvement will have to yield a decrease in continuous migration to 10% in order to be clinic relevant. An alpha level of 0,05 and beta level of 0,20 (power = 80 %) would require 25 cases in each group.

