11.2 Statistical analysis

All variable are considered continuous and measured on an interval scale, except migratory pattern, which is proportional. The difference between the two treatment groups will be evaluated with analysis of variance (ANOVA) for continuous variables at different time periods. Clinical scores will also be analysed using the analysis of covariance (ANCOVA) to compensate for different preoperative starting values. Continuous data which are not normally distributed will be analysed by non-parametric ranking tests and proportional values will be analysed by the chi-square test or the Fischer's exact test at low response frequencies.

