12.3 Ethical committee

The study protocol will be subjected to and approved by the ethical committee of the Medical Faculty, Lund University, before the start of the study.

Amendment No. 2 to Evaluation of Triathlon - a new total knee prosthesis system

3. Number of Subjects

360 patients in six individually randomized sub-studies (30 patients in each randomized group) will be enrolled into the study over a 12 months recruitment period per sub-study.

Study Design Summary Page

- A total of 360 patients will be included in the study, with 30 patients in each group of sub-studies.

**PROTOCOL TITLE:
EVALUATION OF THE TRIATHLON KNEE SYSTEM**

**Protocol addendum - Extended follow-up period with 5, 7 and 10 years
follow-up visits**

Protocol #: K-S-015
Revision: v1.0
Date: 07 May 2014

[figure not shown]
Study responsible doctor

[name]
Dept, Orthop, Hässleholm Hospital
[contact]
e-mail:[contact]

Approved by:

[name]
Clinical Research Director Europe
Stryker SA
[contact]
e-mail: [contact]

Signature: _____

Introduction

The results of knee replacement surgery have continuously improved and operations are now highly cost effective from a social point of view and in terms of improved quality of life for the individual patient. However complications occur, especially in the long term as prosthetic loosening, wear, and infection. Extensive research is on-going to find improved prosthetic materials, better prosthetic design and surgical methods to manage these difficulties.

Adequate surgical expertise and the design of the artificial knee joint are among the most important factors in terms of outcome and long-term results. To evaluate these aspects for the Triathlon prosthesis, it is necessary to collect and analyse data from patients receiving this type of knee prosthesis. By collecting patient information, we can further evaluate some of the overall benefits of modern knee surgery, such as shorter rehabilitation time, generally faster recovery, more natural knee function and improved long-term outcomes. The Triathlon knee system is a further development of both the prosthesis and instrument design. The knee prosthesis design is better adapted to the wide variation of patient anatomy and size.

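### Sub-study g asks whether the short keel is equal to the standard keel, but the plan only tests for a difference, so a non-significant result would leave the question unanswered

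*Combined protocol and SAP*

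**What the plan says.** Section 5 lists eight sub-studies, and g is the one whose aim is worded as equality: "This sub-study is aimed at evaluating if the short tibial keel will have equal fixation and migration properties as the standard keel". The reason given there for the short keel is easier surgery, not better fixation. Section 5 also states: "The principal evaluation parameter will be the RSA". It does not say which RSA measure, or which visit, decides.

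Section 11.1 sizes all sub-studies on two improvement targets. The first is MTPM, from 1.0 ± 0.5 mm: "Suppose this migration will decrease by 50% to 0.5 ± 0.5 mm", giving 17 per group. The second is continuous migration: "Continuous migration between the 1st and 2nd year follow-up has been found in up to 50% of the cases", with a fall to 10% taken as clinically relevant, giving 25 per group.

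Section 11.2 gives one analysis for all sub-studies: "The difference between the two treatment groups will be evaluated with analysis of variance (ANOVA) for continuous variables at different time periods". Rank tests replace ANOVA when data are not normal. The migratory pattern is handled as a proportion ("All variable are considered continuous and measured on an interval scale, except migratory pattern, which is proportional"), and "proportional values will be analysed by the chi-square test", or by Fisher's exact test when frequencies are low.

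Amendment No. 2 changes the numbers only: "A total of 360 patients will be included in the study, with 30 patients in each group of sub-studies". The 2014 addendum adds visits at 5, 7 and 10 years and EQ-5D, but no analysis rule.

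**The concern.** A test of difference takes equality as its null hypothesis. It can reject equality but cannot confirm it, because p>0.05 does not say how large a difference remains compatible with the data. For the sub-studies that look for an advantage this is the usual arrangement. For g the hoped-for finding is that nothing is lost in fixation, and that is the outcome for which the plan has no rule.

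At stake is what can be said about the short keel if the test is not significant. Without a margin or an interval rule, such a result could be taken as support for equality whether or not the data exclude a deficit that matters. When a real difference exists, noisier or fewer data make that outcome more likely. The 2014 addendum brings RSA visits at 5, 7 and 10 years, so the same question will recur.

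**Working it through.** **Inputs.** From section 11.1: SD 0.5 mm, MTPM difference 0.5 mm, proportions 50% and 10%, alpha 0.05, power 80%. Group size is 25 (sections 3 and 8.1) or 30 (Amendment No. 2). Assumed here: normal data, equal groups, no dropout. The documents give no margin and no dropout rate. The values 0.25, 0.3 and 0.4 mm and 20 points below are illustrative.

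**Step 1: the plan's own figures.**
- MTPM: a two-sample t test with difference/SD = 0.5/0.5 = 1 needs 16.7, so 17 per group, two-sided (power 0.807). One-sided it would need 13.1, so 14.
- Continuous migration: n0 = [1.96·√(2·0.3·0.7) + 0.842·√(0.25 + 0.09)]² / 0.4² = 19.4. With continuity correction, (n0/4)·[1 + √(1 + 4/(0.4·n0))]² = 24.1, so 25 per group, two-sided. One-sided it would be 20.

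The stated 17 and 25 therefore match two-sided tests of difference. The plan does not write two-sided; this is inferred from the sample sizes and from the non-directional tests named. The point does not depend on it.

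**Step 2: what a non-significant MTPM result leaves open.** SE = 0.5·√(2/n), which is 0.141 mm at 25 and 0.129 mm at 30. The 95% half-width is about t·SE: 2.011·0.1414 = 0.284 mm and 2.002·0.1291 = 0.258 mm. The probability of p>0.05 (noncentral t) is:

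| True deficit | 25 per group | 30 per group |
|---|---|---|
| 0.5 mm | 7% | 3% |
| 0.25 mm (illustrative) | 59% | 52% |

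At a true difference of 0, about 96%/99% of non-significant results (25/30 per group) have an upper 95% limit below 0.5 mm, but only 55%/63% have it below 0.3 mm. So p>0.05 alone does not say what has been excluded.

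**Step 3: the effect of noise.** At a true difference of 0, p>0.05 occurs 95% of the time whatever the SD or n. With a true 0.25 mm deficit and 25 per group it occurs 59% of the time at SD 0.5 mm and 86% at SD 1.0 mm (assumed).

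**Step 4: continuous migration.** The plan's own 40-point contrast (50% v 10%) has exact Fisher power of 0.833 at 25 and 0.914 at 30, so it is missed 17%/9% of the time. An illustrative true increase of 20 points, from bases of 10% to 50%, is missed 55–77% of the time at 25 and 50–74% at 30, depending on the base rate and on chi-square or Fisher.

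**Step 5: power of an interval rule, true difference 0, margin 0.4 mm.**
- Non-inferiority (upper 95% limit below the margin): noncentrality 0.4/SE = 2.83 at 25 and 3.10 at 30, giving power 0.791/0.861.
- Equivalence (both 95% limits within the margin): by symmetry about 2·0.791 − 1 = 0.58 and 2·0.861 − 1 = 0.72.
- Equivalence by a 90% interval: 0.75/0.84.

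At a 0.3 mm margin, non-inferiority power is 55%/63%.

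**Step 6: why the interval level matters.** Take a 0.4 mm margin, 25 per group and a keel truly 0.25 mm worse. Equivalence by a 90% interval is declared 27% of the time, non-inferiority by a 95% interval 18%. With mixed levels, the stronger claim is the easier one to reach. With the same 95% interval for both this cannot happen, because equivalence adds a second condition.

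**The case against.** The best defence is that the trial is informative anyway. The only MTPM effect in the documents is 0.5 mm; a deficit of that size is rarely missed, and when the keels are truly equal nearly all non-significant results exclude it. That stands, and a reader who inferred that g is too small to be useful would go beyond the documents. But section 11.1 uses 0.5 mm, half the reference migration, as an improvement target and nowhere as an acceptable loss. The less favourable figures rest on values that the documents do not contain, so they show sensitivity and do not establish a failure.

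A reader might also infer that the plan will declare equality when p>0.05. It says no such thing, and section 11.2 does not forbid reporting estimates with intervals. The harm is a risk of misreading. Nor is it right that g cannot answer its question at all: a significant difference answers it, in the negative. Only the non-significant outcome lacks a rule.

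Finally, it may be too late to fix a margin in advance. The 2014 addendum speaks favourably of results already collected, without saying which sub-studies they cover. That affects how the margin must be reported; it does not remove the gap.

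**Conclusion.** The point holds, for sub-study g alone. The aim is equality, the sample size and the tests concern a difference, and no margin or interval rule bridges the two. Followed as written, the analysis can show that the keels differ but cannot establish that they are equal. It should be fixed, although randomisation and data collection are unaffected.

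How much this matters depends on the deficit that is clinically important, which the documents do not state. If it is 0.5 mm, the design seldom misses it (7%/3% at 25/30 per group). If it is nearer 0.25 mm, a non-significant result is more likely than not (59%/52%). These figures rest on SD 0.5 mm, normal data, two-sided 5% tests and no dropout. That the textual gap exists depends on none of them.

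**What to change.** For sub-study g only:

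1. Make the deciding analysis a 95% confidence interval for the difference in 2-year MTPM, short minus standard keel. The documents name the primary variable only as RSA; 2-year MTPM is proposed because section 11.1 uses it, and the choice should be stated.
2. Judge the interval against a clinically justified margin that the sponsor chooses and fixes before g's outcome data are examined. If they have already been seen, report the margin as set afterwards.
3. State whether the claim is equivalence (both limits within the margin) or non-inferiority (upper limit below it). If non-inferiority, amend the word equal in section 5.
4. Use the same 95% interval for either claim, or disclose that a 90% interval for equivalence uses a looser error rate per side (5% instead of 2.5%).
5. Report the difference in the proportion with continuous migration between years 1 and 2 with its confidence interval.
6. State that p>0.05 on either measure will not be read as equality.
7. State the power of the chosen rule in section 11.1.

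The cost is wording and one margin to agree, with no new data. The price is a stricter rule. At 25/30 per group an illustrative 0.4 mm margin has 79%/86% power for non-inferiority, but only about 58%/72% for equivalence by the 95% interval (75%/84% by the 90% interval). For a tighter margin the lower power should be stated. For scale, 80% power for non-inferiority at 0.3 mm would need 45 per group.

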6.1 Inclusion criteria

1. Patients suffering exclusively from OA, Stage II-V [Ahlbäck, 1968 #391] will be operated.
2. Patients requiring knee prosthesis, suitable for the use of Duracon and Triathlon knee system
3. Patients who understand the conditions of the study and are willing and able to comply with the post-operative scheduled clinical and radiographical evaluations and the prescribed rehabilitation.
4. Patients who signed the Ethics Committee approved Informed Consent Form prior to surgery.

